9.6.1.2. Classifications for adverse event assessment

All AEs will be assessed and documented by the investigator according to the categories detailed below.

9.6.1.2.1. Seriousness

For each AE, the seriousness must be determined according to the criteria given in Section [9.6.1.1](#).

9.6.1.2.2. Intensity

The intensity of an AE is classified according to the following categories:

- Mild – usually transient in nature and generally not interfering with normal activities
- Moderate – sufficiently discomforting to interfere with normal activities
- Severe – prevents normal activities

9.6.1.2.3. Causal relationship

The assessment of the causal relationship between an AE and the administration of treatment is a decision to be made by the investigator, who is a qualified physician, based on all information available at the time of the completion of the eCRF.

Causality should be assessed separately for each study treatment as detailed in the eCRF. If the investigator feels that the event cannot be firmly attributed to one of the study treatments (e.g. owing to a suspected underlying interaction), the same assessment will be documented for each study treatment.

The assessment is based on the question whether there was a “reasonable causal relationship” to the study treatment in question.

Possible answers are “yes” or “no”

An assessment of “no” would include:

1. The existence of a highly likely alternative explanation, e.g. mechanical bleeding at surgical site.

OR

2. Non-plausibility, e.g. the subject is struck by an automobile when there is no indication that the drug caused disorientation that may have caused the event; cancer developing a few days after the first drug administration.

An assessment of “yes” indicates that the AE is reasonably associated with the use of the study treatment strategy. Important factors to be considered in assessing the relationship of the AE to study treatment include:

- The temporal sequence from drug administration: The event should occur after the drug is given. The length of time from drug exposure to event should be evaluated in the clinical context of the event.
- Recovery on drug discontinuation (de-challenge), recurrence on drug re-introduction (re-challenge): Subject’s response after de-challenge or re-challenge should be considered in view of the usual clinical course of the event in question.

- Underlying, concomitant, intercurrent diseases:
Each event should be evaluated in the context of the natural history and course of the disease being treated and any other disease the subject may have.
- Concomitant medication or treatment:
The other drugs the subject is taking or the treatment the subject receives should be examined to determine whether any of them might have caused the event in question.
- Known response pattern for this class of drug: clinical/preclinical
- Exposure to physical and/or mental stresses: The exposure to stress might induce adverse changes in the recipient and provide a logical and better explanation for the event
- The pharmacology and pharmacokinetics of the study treatment:
The pharmacokinetic properties (absorption, distribution, metabolism and excretion) of the study treatment, coupled with the individual subject's pharmacodynamics should be considered.
- The assessment is not possible

Causal relationship to protocol-required procedure(s)

The assessment of a possible causal relationship between the AE and protocol-required procedure(s) is based on the question whether there was a “reasonable causal relationship” to protocol-required procedure(s).

Possible answers are “yes” or “no”

9.6.1.2.4. Action taken with study treatment

Any action on study treatment to resolve the AE is to be documented using the categories listed below.

The study treatment action should be recorded separately for each study treatment as detailed in the eCRF.

- Drug withdrawn
- Drug interrupted
- Dose reduced
- Dose not changed
- Dose increased
- Not applicable
- Unknown

9.6.1.2.5. Other specific treatment(s) of adverse events

- None
- Remedial drug therapy

- Other

9.6.1.2.6. Outcome

The outcome of the AE is to be documented as follows:

- Recovered/resolved
- Recovering/resolving
- Recovered/resolved with sequelae
- Not recovered/not resolved
- Fatal
- Unknown

9.6.1.3. Assessments and documentation of adverse events

The investigator has to record on the respective eCRF pages adverse events as described under Section [9.6.1.1](#) occurring in the period between the signing of the IC and the end of the follow-up phase; after the end of the clinical follow-up phase there is no requirement to actively collect AEs including deaths. The type of information that should be assessed and recorded by the investigator for each AE is listed in Section [9.6.1.2](#).

“Death” should not be recorded as an AE on the AE page. Instead, “death” is the outcome of underlying AE(s).

For all serious adverse events (SAEs) the sponsor has to carry out a separate assessment for expectedness, seriousness, and causal relationship to study drug.

9.6.1.4. Reporting of SAEs/ AEs

The definition of serious adverse events (SAEs) is given in Section [9.6.1.1](#).

The following detailed rules apply to AE and SAE handling and are provided in [Figure 3](#) below:

- Primary or secondary efficacy endpoints, including all-cause death, have to be recorded on Efficacy Endpoint pages of the eCRF. Only non-cardiovascular (non-CV) death has to be reported as SAE within 24 hours of the investigator’s awareness. All other primary and secondary efficacy endpoints are exempted from expedited reporting.
- All primary and secondary safety endpoints (i.e. bleedings) have to be recorded in the eCRF. Only pericardial bleedings and pulmonary alveolar bleedings/ pulmonary bleedings, which are defined as AEs of special interest (see also Section [9.6.1.6](#)), have to be reported within 24 hours of the investigator’s awareness even if classified as non-serious. All other primary and secondary safety endpoints are exempted from expedited reporting.
- All other events (including complications of efficacy or safety endpoints events) that fulfill the seriousness criteria have to be recorded on the AE page of the eCRF and reported within 24 hours of the investigator’s awareness.

[figure not shown]

- All pregnancies in female study subjects or in female partner of a male study subject as well as endpoints of the pregnancies have to be reported within 24 hours of the investigator's awareness. For pregnancy reports, the Pregnancy Monitoring Forms are to be used.
- Non-serious AEs that lead to permanent study drug discontinuation have to be recorded on the AE page of the eCRF but do not require further reporting. Non-serious AEs which DO NOT lead to discontinuation of study medication DO NOT NEED to be recorded and reported. However, non-serious AEs that the investigator considers of particular concern may be recorded on the AE page of the eCRF to bring them to the attention of the sponsor.
- Of the AEs reported, reportable events (i.e. SUSARs) have to be reported to the competent authorities and to the Independent IECs/IRBs according to legal requirements.

If reported, SAEs occurring after the protocol-defined observation period will be processed by the sponsor according to all applicable regulations.

The investigator must report immediately (within 24 hours of the investigator's awareness) all SAEs described above as requiring expedited reporting. The report recipients are detailed in the instructions for SAE reporting included in the Investigator File.

The investigator is responsible for continuous monitoring of all SAE reports (whether or not related to study drug) until resolution or until the event is considered chronic and/or stable by the investigator and/or other physician who has the responsibility for the subject's medical care. Follow-up SAE reports will be reported according to the same timelines as initial reports, as soon as new significant information becomes available.

Figure 3: Outcome and (S)AE collection and reporting schematic

9.6.1.5. Expected adverse events

For this study, the applicable reference document is the most current version of the investigator's brochure (IB) / summary of product characteristics.

The following events are expected to occur with TAVR and therefore should not be reported as AEs, unless they occur outside of the stated timeframe:

- Back pain related to laying on the procedure table within 3 days after TAVR
- Incisional pain (pain at access site) within 3 days after TAVR
- Sleep problems or insomnia within 7 days after TAVR
- Mild to moderate bruising or ecchymosis within 7 days after TAVR.

9.6.1.6. Adverse events of special safety interest

The following events are considered as AEs of special interest:

- Pericardial bleedings
- Pulmonary alveolar bleedings/pulmonary bleedings

These AEs (even if classified as non-serious) have to be reported within 24 hours of the investigator's awareness by recording them on the AE page of the eCRF.

9.6.2. Pregnancies

The reporting of pregnancies is described in Section [9.6.1.4](#).

9.6.3. Further safety

9.6.3.1. Laboratory evaluations

This section was modified with Amendment 3. For details, see Section [15.2](#).

The following local routine laboratory measurements need to be evaluated before randomization:

- Hematology tests
 - Hemoglobin
 - Platelet count
 - White cell count
- Liver tests
 - Transaminases (AST/ALT)
 - Total bilirubin and components (conjugated and/or unconjugated fractions in case of elevated total bilirubin)
 - Alkaline phosphatase, if available as current standard of care
- Renal function
 - Creatinine clearance (CrCl).

Serum creatinine levels in order to derive the estimated creatinine clearance (mL/min/1.73m²) using the MDRD formula. If serum creatinine levels are not available the estimated creatinine clearance (mL/min/1.73m²) as reported in lab printout should be selected.

Laboratory tests results done as part of standard of care can be used. Hematology tests and renal function results from standard of care can be used as long as collected after the index-TAVR procedure and before randomization. Liver test results collected before TAVR procedure can be used as long as performed as part of the standard of care for the index-TAVR procedure.

For all the laboratory evaluations described above, if multiple values are available, the measurement closest to the visit date should be selected.

9.6.3.2. Physical examination

A targeted physical examination of the cardiovascular and neurological systems will be performed and relevant information will be recorded in the eCRF.

Abnormal physical examination findings are recorded either as medical history or as adverse events (see Section 9.6.1.1).

9.6.3.3. 12-lead ECG

Standard 12-lead ECGs will be performed locally as depicted in the schedule of evaluations (Section 9.1) and pertinent information will be recorded in the eCRF. Copies of all recorded ECGs are stored in the patient hospital files.

9.6.3.4. Vital signs

For vital signs the following parameters will be recorded:

- Heart rate
- Blood pressure
- Weight
- Height (only at screening)

9.7. Other procedures and variables

Echocardiography

Findings from routine echocardiograms (either TTE or TEE) will be collected post-TAVR and at approximately 360 days after randomization (360 ± 90 days or last available between 180-360 days) if available according to the local standard of care for TAVR. Selected hemodynamic parameters will be recorded in the eCRF. Copies of recorded echocardiograms are stored in the patient hospital files.

If an investigational study center is routinely collecting 3D TEE in their post-TAVR subjects, these recordings may be used as the scheduled echocardiograms described above, as long as the sponsor/designated CRO is informed and has approved it accordingly.

9.8. Appropriateness of procedures / measurements

The measurements and procedures chosen for this study are widely used, and generally recognized as reliable and accurate.

10. Statistical methods and determination of sample size

10.1. General considerations

A general description of the statistical methods to be used to analyze the efficacy and safety of the study drug is outlined below. A more detailed statistical analysis plan (SAP) will be provided in a separate document. Statistical analysis will be performed using SAS; the version used will be specified in the SAP. The SAP will accommodate protocol amendments or unexpected issues in study execution or data that affect planned analyses, and will provide

more details on the analytic approaches, coding guidelines, censoring of time-to-event variables, and output tables and figures.

If not stated otherwise, all efficacy and the safety analyses will be based on findings as confirmed by the Clinical Event Committee (CEC). Definitions of terms and endpoints are located in Sections [16.1](#) and [16.2](#).

10.2. Analysis sets

10.2.1. Full analysis set (FAS)

Both the efficacy analysis and the safety analysis are based on the population of all randomized subjects. In accordance with the International Conference on Harmonization (ICH) E9 guidelines, the population of all randomized subjects is termed the Full Analysis Set (FAS).

Subjects are categorized according to the group to which they were assigned by the randomization process.

10.2.2. Data scopes

This section was modified with Amendment 3. For details, see Section [15.2](#).

The following data scopes are defined for efficacy and safety analyses.

Data scope according to intention-to-treat principle (ITT analysis)

The ITT data scope includes all outcome events observed from randomization until the efficacy cut-off date (i.e. the day of the primary completion event). The follow-up period for each subject will be as long and complete as possible between randomization up to the visit scheduled after the anticipated efficacy cut-off date is set.

Data scope according to treatment (OT analysis)

The on-treatment data scope includes all outcome events observed from randomization until two days following permanent discontinuation of the randomized treatment strategy. Subjects are off the rivaroxaban-based treatment strategy when rivaroxaban has been permanently discontinued. Subjects are off the antiplatelet-based treatment strategy when both clopidogrel and ASA have been permanently discontinued within the first 3 months or when ASA alone has been permanently discontinued after 3 months, except in case of NOAF and receiving VKA.

Data scope until NOAF (pre-NOAF analysis)

The pre-NOAF data scope includes all outcome events observed from randomization until the NOAF requiring (a switch to) treatment with high dose rivaroxaban or vitamin K antagonists.

Data scope after NOAF (post-NOAF analysis)

The post-NOAF data scope includes all outcome events observed between the treatment switch precipitated by NOAF until the efficacy cut-off date.

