7.1.2.1. After NOAF

- First 90 days:
 - Open-label VKA therapy to target INR 2-3, according to guidelines.

- Clopidogrel 75 mg once-daily is discontinued.
- ASA 75-100 mg once-daily is continued unchanged.
- After the first 90 days:
 - Open-label VKA therapy alone to target INR 2-3.
 - Clopidogrel 75 mg once-daily must remain discontinued.
 - ASA 75-100 mg once-daily is discontinued.

Initiation of VKA therapy will be performed according to the summary of product characteristics (SPC) or relevant product label for the respective VKA. INR values will be measured according to local standard of practice. The investigator should assess if a parenteral anticoagulant drug (such as low molecular weight heparin) for bridging purposes is needed in addition to VKA therapy as per standard of care until the target INR of at least 2.0 is achieved.

In case NOAF is diagnosed and the patient refuses to switch to the full oral anticoagulation as described above (whether rivaroxaban 20/15 mg once-daily in the rivaroxaban-based strategy or VKA in the antiplatelet-based strategy), the patient may remain on the study treatment assigned before NOAF for the remaining duration of the study if the treating physician considers it safe and the clinical situation allows doing so (58, 59).

In case atrial flutter is diagnosed after randomization with an ongoing indication for full oral anticoagulant treatment, the choice of the full anticoagulation should follow the treatment recommendation for NOAF as per the assigned treatment strategy and described above.

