10.3.5.3. Exploratory analyses of the primary efficacy variable

In the primary analyses, switches to full dose anticoagulation are treated as integral part of the treatment strategy. Pre-NOAF analyses, with censoring at the time of the switch to anticoagulation therapy, are carried out as exploratory analyses. Post-NOAF analyses, with starting at the time of the treatment switch precipitated by NOAF are carried out as exploratory analyses.

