5.2.3 Data scope pre-NOAF analysis

Date of NOAF requiring treatment with high dose oral anticoagulation

Date NOAF is defined as the date where treatment with high dose oral anticoagulation for NOAF is started. Information is derived from study drug exposure form for Rivaroxaban or VKA in combination with ECG evidence of NOAF.

Censoring of follow-up in pre-NOAF analysis

Censoring of follow-up for subjects is on the efficacy cut-off date, date of last known visit or NOAF date, whichever comes first.

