5.2.4 Data scope post-NOAF analysis

Date of NOAF requiring treatment with high dose oral anticoagulation

Date NOAF is defined as the date where treatment with high dose oral anticoagulation for NOAF is started. Information is derived from study drug exposure form for Rivaroxaban or VKA in combination with ECG evidence of NOAF.

Start of follow-up in post-NOAF analysis

Day 1 in post NOAF analysis is the date of NOAF as defined above.

Censoring of follow-up in post-NOAF analysis

Censoring of follow-up for subjects is on the efficacy cut-off date, or date of last known visit, whichever comes first.

Only subjects that start OAC treatment as described in the protocol section 7.1.1.1 and 7.1.2.1 are included from the post-NOAF analysis.

6. Statistical Methodology

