6.5 Other analysis

Pre-NOAF and post-NOAF analysis are carried out as an exploratory analysis for the primary efficacy variable (DTE). On treatment, pre-NOAF and post-NOAF analysis are carried out as an exploratory analysis for the primary safety (PBE) variable. The analyses are done analogue to the superiority HR analysis as described in [6.2.1.2](#) and are visualized in [flowchart 4](#).

The separate components of the adjudicated primary efficacy and safety endpoint are analyzed exploratory and analogue to the superiority HR analysis as described in [6.2.1.2](#). The separate components of the adjudicated primary efficacy and safety endpoint are:,

- All-cause death
- Any stroke
- Myocardial infarction
- Symptomatic valve thrombosis
- Pulmonary embolism
- Deep vein thrombosis
- Non-CNS systemic embolism
- Life-threatening or disabling bleeds (BARC type 3b, 3c or 5)
- Major bleeds (BARC type 3a).

The following details of NOAF are summarized by treatment:

- Subjects with NOAF reported on ECG but without medication switch
- Subjects with medication switch but without ECG evidence of NOAF
- Subjects with both ECG evidence and medication switch

Medication switch here means: requiring treatment with high dose oral anticoagulation as specified in 3.2.

Mean transaortic valve pressure gradient is measured by echocardiogram (TTE or TEE) at screening and at approximately 360 days after randomization. The difference between 360 days and screening is derived and analyzed exploratory by using a t-test.

The analysis the other variables are visualized in [flowchart 2](#) in appendix I.

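### The exploratory pre- and post-NOAF analyses are dated from the anticoagulant switch, so subjects with AF who do not switch stay in pre-NOAF, and an event that prompts a same-day switch is attributed to the new drug

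*Protocol*

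**What the plan says.** The post-NOAF scope in Protocol 10.2.2 begins at the switch: "The post-NOAF data scope includes all outcome events observed between the treatment switch precipitated by NOAF until the efficacy cut-off date". The same section ends the pre-NOAF scope less clearly, with events counted "until the NOAF requiring (a switch to) treatment with high dose rivaroxaban or vitamin K antagonists". Protocol 10.3.5.3 settles the meaning: "Pre-NOAF analyses, with censoring at the time of the switch to anticoagulation therapy, are carried out as exploratory analyses".

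SAP 5.2.3 agrees: "Date NOAF is defined as the date where treatment with high dose oral anticoagulation for NOAF is started". It censors pre-NOAF follow-up on that date, or earlier at the efficacy cut-off or last known visit. SAP 5.2.4 uses the same date to open the next period: "Day 1 in post NOAF analysis is the date of NOAF as defined above". It also restricts who enters: "Only subjects that start OAC treatment as described in the protocol section 7.1.1.1 and 7.1.2.1 are included from the post-NOAF analysis".

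Protocol 7.1.2.1 foresees NOAF without a switch. If the patient refuses full anticoagulation and the treating physician considers it safe, "the patient may remain on the study treatment assigned before NOAF for the remaining duration of the study". SAP 6.5 tabulates this group by treatment ("Subjects with NOAF reported on ECG but without medication switch") but gives no rule for analysing it.

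The pre- and post-NOAF analyses are exploratory for both the efficacy endpoint (DTE) and the bleeding endpoint (PBE) (Protocol 10.3.5.3 and 10.3.7; SAP 6.5).

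**The concern.** These are the only planned analyses that separate 10 mg rivaroxaban against antiplatelet therapy from 20/15 mg rivaroxaban against a VKA. Readers will look to them for what happens before and after AF.

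Two features make that reading unsafe. First, the pre-NOAF comparison contains AF time, both between the ECG and the switch and for subjects who never switch. The post-NOAF comparison contains only those who accepted the switch. Accepting means another tablet strength of the same drug in one arm (Protocol 7.1.1.1), and starting a VKA with INR control and possible bridging in the other (7.1.2.1). Treatment is open-label (7.5), so acceptance could depend on both arm and prognosis.

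Second, a stroke may be what reveals AF and prompts the switch. If the new drug starts that day, the stroke falls on post-NOAF Day 1 and is attributed to a drug it preceded.

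**Working it through.** The documents state no figure for these analyses, so there is none to reproduce. The check applies the date rules to examples and then asks what can be said about size.

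**1. Date rules.** All four subjects have AF on ECG at day 10 after randomisation.

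| Switch | DTE | Pre-NOAF | Post-NOAF |
|---|---|---|---|
| day 20 | day 15 | counted, although AF is documented | not counted |
| none | day 50 | counted, although AF is documented | never enters |
| day 20 | day 20 | counted only if the censor date is inclusive | counted |
| day 20 | day 21 | not counted | counted |

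SAP 5.2.3 does not say whether its censor date is inclusive. Nearby conventions suggest that it is: the ITT scope in Protocol 10.2.2 runs to the day of the last counted event, and SAP 5.2.1 lists date of death as a censoring date although death is an endpoint. On either reading, the day-20 event counts in post-NOAF.

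**2. Numbers affected.** Inputs: 1520 randomised (Protocol synopsis); NOAF in up to 30% (Protocol 10.4). Assumed: NOAF in 10 to 30%, and 5 to 30% of those not switching.
- NOAF: 1520 × 0.10 = 152, to 1520 × 0.30 = 456.
- Not switching: 152 × 0.05 ≈ 8, to 456 × 0.30 ≈ 137.
- Entering post-NOAF: 152 × 0.70 ≈ 106, to 456 × 0.95 ≈ 433.

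**3. Selection with no true effect.** All inputs are assumed: a share 0.30 of subjects is frail, with relative hazard h = 1.5 to 3, and every refuser is frail, which is extreme. With refusal share r, the mean relative hazard of acceptors when post-NOAF follow-up starts is [0.70 + (0.30 − r)h] / (1 − r).
- r = 0.10: (0.70 + 0.20h)/0.90 = 1.11 (h = 1.5) to 1.44 (h = 3).
- r = 0.30: 0.70/0.70 = 1.00.
- Refusal 10% on rivaroxaban and 30% on control: ratio 1.11 to 1.44.
- The reverse: 1/1.11 = 0.90 to 1/1.44 = 0.69.
- Refusal 20% in both arms: ratio 1.00.

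The sign depends entirely on which arm refuses more, and the documents do not say.

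**4. Same-day events.** Control hazard from Protocol 10.4: −ln(1 − 0.33)/540 = 0.000742 per day. Assumed: hazard 1.5 times higher after NOAF, 300 days of later follow-up, and a proportion p of switches falling on the day of a DTE.
- Later event probability q = 1 − exp(−0.000742 × 1.5 × 300) = 0.284.
- Share of post-NOAF first events that are same-day: p / [p + (1 − p)q].
- p = 0.02: 0.02/(0.02 + 0.278) ≈ 7%. p = 0.10: 0.10/(0.10 + 0.255) ≈ 28%.

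The share is driven by p, which the documents do not give.

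**The case against.** **The analyses are exploratory.** They lie outside the testing hierarchy, and the primary analysis treats switches as part of the strategy. This stands in full.

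**The switch date is the right anchor for comparing regimens.** An ECG anchor would put unswitched 10 mg or antiplatelet time into post-NOAF, and the question would become one of strategy after AF. This also stands, so the switch-based analysis should not be replaced. Nor would an ECG anchor remove selection: recorded AF is itself a post-randomisation event in an open-label trial.

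**The bias is hypothetical and small beside sampling error.** With 106 to 433 subjects and q = 0.284, there would be about 30 to 123 post-NOAF events. With equal arms, the 95% limits are the hazard ratio multiplied or divided by exp(1.96 × 2/√d), which is 2.05 at d = 30 and 1.42 at d = 123. Most of the range in step 3 lies inside that. This stands as a limit on importance, although a confidence interval does not allow for selection bias.

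**SAP 6.5 already tabulates non-switchers by arm.** Differential refusal would therefore be visible. That helps a reader suspect a problem, but it does not provide an analysis that includes those subjects.

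**Two stronger readings fail.** A reader might infer that a switch-date event is certainly counted twice. That needs an inclusive pre-NOAF censor date, which SAP 5.2.3 does not state, and the two scopes are never added together. A reader might also infer that post-NOAF reuses time to first DTE since randomisation, so that an earlier DTE would precede Day 1. SAP 6.5 asks only for an analysis analogous to 6.2.1.2, the code there is optional, and 5.2.4 resets Day 1. What remains is that the handling of an earlier event is unstated.

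**Conclusion.** The point holds as a matter of definition and interpretation. Both scopes are dated from the start of high-dose anticoagulation. Subjects with documented NOAF who do not switch stay in pre-NOAF, and post-NOAF compares only those who start the anticoagulant. An event that led to a same-day switch is attributed to the new drug on either reading of the censor date.

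No size or direction can be derived from the documents. A reader might infer that the post-NOAF hazard ratio is biased against rivaroxaban, but that requires assuming more refusal, by frailer subjects, in the control arm. The opposite assumption reverses the sign, and equal refusal gives none. The figures in steps 2 to 4 illustrate assumptions and are not estimates.

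The primary non-inferiority and superiority tests and the type I error are unaffected. The case for acting is that the corrections are cheap and these analyses will be read as evidence on the two regimens.

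**What to change.** Amend SAP 5.2.3, 5.2.4 and 6.5:

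- Count events on or before the switch date as pre-NOAF. Start post-NOAF follow-up on the following day.
- In post-NOAF, count the first DTE or PBE after that start, including for subjects with an earlier event.
- Keep the switch-based analysis, which separates the regimens.
- Add a companion analysis dated from the first ECG-documented NOAF, for all such subjects whether or not they switch.
- State that the post-NOAF hazard ratio compares groups selected after randomisation.

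The cost is SAP wording and a little programming. No clinical rule changes. The companion analysis mixes switched and unswitched time, so it should be read beside the switch-based one. It also needs a rule for incomplete ECG dates: SAP 4.3 gives an assurance of complete dates only for the medication dates used in the data scopes.
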